6.5. Concomitant Therapy

The use of any concomitant medication, prescription or over-the-counter, is to be recorded on the subject's electronic case report form (eCRF) at each visit along with the reason the medication is taken, the dates of administration, and the dose.

6.5.1. Prohibited Drugs and Washout Before the Study

Section 10.6 provides a listing of specific restrictions for concomitant therapy use during the study, with any necessary washout periods described and examples of prohibited drug categories. If there is a clinical indication for any therapy that is specifically prohibited during the study, discontinuation from Study Treatment may be required. The investigator should discuss any questions regarding this with the Sponsor's representing Medical Monitor. The final decision on any supportive therapy rests with the investigator and/or the subject's primary physician. However, the decision to continue the subject on Study Treatment requires the mutual agreement of the investigator and the Sponsor's designated Medical Monitor.

Consult the Sponsor's designated Medical Monitor if there is any uncertainty regarding subject use of a particular drug or drug class.

6.5.2. Permitted Drugs

With the exception of the agents described in Section 10.6, any other concomitant medication deemed necessary for the welfare of the subject during the study may be given at the discretion of the investigator. If the permissibility of a specific medication/drug is in question, please contact the Sponsor's designated Medical Monitor. Any medication or vaccine (including over-

the-counter or prescription medicines, vitamins, and/or herbal supplements) that the subject is receiving at the time of enrollment or receives during the study must be recorded in the eCRF.

6.6. Dose Modification

No dose modification of study drug is permitted. Study drug should be withheld for liver test abnormalities as described in [Section 8.4.6.2](#).

6.7. Drug After the End of the Study

Subjects who complete the study through the Week 24 Visit may be offered the opportunity to enroll in a 28-week extension study (URO-901-3006), in which open-label vibegron will be provided.

7. Discontinuation of Study Drug and Subject Discontinuation or Withdrawal

A premature discontinuation will occur if a subject who signs the informed consent form (ICF) and is randomized ceases participation in the study, regardless of circumstances, before the completion of the protocol-defined study procedures.

7.1. Discontinuation of Study Drug

Subjects who discontinue study drug will complete the Week 24/Early Withdrawal assessments specified in the Schedule of Assessments ([Section 1.3](#) and [Section 1.4](#)).

Reasons for discontinuation from the study drug include the following:

- Any AE of urinary retention
- Any occurrence of PVR volume \geq 300 mL

Discontinuation of study drug for abnormal liver function should be considered by the investigator when a subject meets all of the conditions outlined in [Section 8.4.6.2](#) for Hy's law or if the investigator believes that it is in the best interest of the subject (reason for discontinuation will be AE).

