 - For subjects with systolic blood pressure \geq 140 mmHg **OR** diastolic blood pressure \geq 90 mmHg at **baseline** (Visit 3):
An increase, compared to baseline (Visit 3) at **2 consecutive visits**, in the average of 3 systolic blood pressures by \geq 20 mmHg **or** 3 diastolic blood pressures by \geq 10 mmHg
 - Initiation or increase in dose of medication for treatment of hypertension in any subject

Note 1: The onset date for an AESI hypertension is the first of the dates when the event meets any of the above criteria.

Note 2: An *AE of “increased blood pressure”* should be recorded if, in the investigator’s opinion, an elevated blood pressure measurement is clinically significant but does not fulfill the above definition for hypertension.

- Adverse events consistent with **orthostatic hypotension** as confirmed by orthostatic vital signs
- **Elevated serum aspartate aminotransferase (AST) or alanine aminotransferase (ALT)** lab value requiring that study drug be temporarily withheld or permanently discontinued (see [Sections 8.4.6.1](#) and [8.4.6.2](#)). To date, no concern regarding drug-induced liver toxicity has been identified; however, the Sponsor is monitoring laboratory data for a potential safety signal, consistent with Food and Drug Administration guidance [[FDA Guidance, 2009](#)].
- **Neoplasms**

Serious AESIs and elevated liver enzymes or bilirubin requiring withholding of study drug (see [Section 8.4.6.1](#)) must be reported within 24 hours of the study site personnel's knowledge of the event by marking the appropriate box on the AE eCRF and assigning the most appropriate category. Additional information should be provided as directed in the eCRF Completion Guidelines. AESIs that also meet the definition of an SAE must be reported as an SAE, as described in [Section 8.4.4](#). Nonserious AESIs should be reported within 72 hours of the site personnel's knowledge, using the AE eCRF.

8.4.6.1. Criteria for Temporary Withholding of Study Treatment in Association with Liver Test Abnormalities

Elevated liver enzymes or bilirubin sufficient to require withholding study medication must be reported **within 24 hours of the study site personnel's knowledge of the event** using AESI specific eCRFs/forms/worksheets provided for the study.

Hepatic enzymes will be monitored in accordance with FDA drug-induced liver injury guidelines [[FDA, 2009](#)].

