If **any** of the following liver test abnormalities develop, study drug should be withheld immediately with appropriate clinical follow-up (including repeat laboratory tests, until a subject's laboratory profile has returned to normal/baseline status), and the event reported as an SAE:

- ALT or AST $> 8 \times$ upper limit of normal (ULN)
- ALT or AST $> 5 \times$ ULN and persists for more than 2 weeks
- ALT or AST $> 3 \times$ ULN and total bilirubin $> 2 \times$ ULN or international normalized ratio (INR) > 1.5
- ALT or AST $> 3 \times$ ULN with appearance of fatigue, nausea, vomiting, right upper quadrant pain or tenderness, fever, rash and/or eosinophilia ($> 5\%$)

Rechallenge may be considered if an alternative cause for the abnormal liver tests (ALT, AST, total bilirubin) is discovered and the laboratory abnormalities resolve to normal or baseline values. The investigator and Sponsor's designated Medical Monitor must discuss and agree with any decision to rechallenge.

Rechallenge should not occur when the etiology of the liver test abnormalities is considered possibly drug-induced.

8.4.6.2. Criteria for Permanent Discontinuation of Study Treatment in Association with Liver Test Abnormalities

Study treatment should be discontinued permanently if **all** of the following 4 criteria are met (ie, potential severe drug-induced liver injury/Hy's law case):

- Total bilirubin increases to $> 2 \times$ ULN or INR > 1.5 **and**
- AST or ALT increases to $\geq 3 \times$ ULN **and**
- Alkaline phosphatase value does not reach $2 \times$ ULN **and**

- No alternative cause explains the combination of the above laboratory abnormalities; important alternative causes include, but are not limited to the following:
 - Hepatobiliary tract disease
 - Viral hepatitis (eg, hepatitis A/B/C/D/E, Epstein-Barr virus)
 - Exposure to hepatotoxic agents/drugs or hepatotoxins, including herbal and dietary supplements, plants, and mushrooms
 - Alcoholic hepatitis
 - Non-alcoholic steatohepatitis
 - Autoimmune hepatitis

If an alternative cause for hepatotoxicity is identified, then it should be determined (based on the severity of the hepatotoxicity or event) whether study drug should be withheld or permanently discontinued as appropriate for the safety of the subject, following consultation with the Sponsor's designated Medical Monitor.

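### Protocol 6.6 sends temporary withholding for liver tests to the permanent-discontinuation rule, and 7.1 makes discretionary the Hy's-law stop that 8.4.6.2 directs

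*Protocol*

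**What the plan says.** Four places in the Protocol bear on this.

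- **6.6 Dose Modification:** "Study drug should be withheld for liver test abnormalities as described in" Section 8.4.6.2.
- **7.1 Discontinuation of Study Drug:** "Discontinuation of study drug for abnormal liver function should be considered by the investigator" in either of two situations: the subject meets every 8.4.6.2 condition for Hy's law, or the investigator judges stopping to be in the subject's best interest.
- **8.4.6.1**, headed "Criteria for Temporary Withholding of Study Treatment in Association with Liver Test Abnormalities": if any one of four abnormalities develops, "study drug should be withheld immediately with appropriate clinical follow-up", and the event is reported as an SAE. On return to drug: "Rechallenge may be considered if an alternative cause for the abnormal liver tests" is found and the values resolve, with the Medical Monitor's agreement.
- **8.4.6.2**, on permanent discontinuation: "Study treatment should be discontinued permanently if" all four listed criteria are met. The section labels this a potential Hy's-law case.

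The body of 8.4.6 has the mapping right. It cites 8.4.6.1 for "elevated liver enzymes or bilirubin requiring withholding of study drug", and cites both subsections together where it speaks of drug being either withheld or stopped for good.

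**The concern.** The two subsections use opposite logic: any of four against all of four. A reader who follows only the citation in 6.6 reaches a rule that demands raised bilirubin or INR, no marked rise in alkaline phosphatase and no alternative cause. That reader finds no instruction to withhold drug for an isolated marked ALT or AST rise, or for a symptomatic one.

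Section 7.1 raises a different problem. For one and the same subject it asks the investigator to think about stopping, while 8.4.6.2 directs a permanent stop. Because one verb in 7.1 governs both of its situations, the discretion cannot be read as attaching only to the best-interest judgement. In the same section, urinary retention and PVR of 300 mL or more are listed flatly as reasons to discontinue.

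At stake are the consistency of a hepatic stopping rule across about 135 sites and the status of any Hy's-law subject. Under 7.2, discontinuing study drug also means withdrawing from the study. Withheld or discontinued therefore decides whether he stays in follow-up, when the early-withdrawal assessments fall due, and whether the event enters the table of TEAEs leading to discontinuation (SAP 7.1).

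**Working it through.** The Protocol gives no figure to reproduce here. The check sets the two rules side by side.

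**8.4.6.1, withhold if any one applies**
1. ALT or AST > 8 × ULN
2. ALT or AST > 5 × ULN for more than 2 weeks
3. ALT or AST > 3 × ULN, and bilirubin > 2 × ULN or INR > 1.5
4. ALT or AST > 3 × ULN "with appearance of fatigue, nausea, vomiting, right upper quadrant pain or tenderness, fever, rash and/or eosinophilia" (> 5%)

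**8.4.6.2, discontinue permanently if all apply**
1. Bilirubin > 2 × ULN or INR > 1.5
2. ALT or AST ≥ 3 × ULN
3. Alkaline phosphatase (ALP) below 2 × ULN
4. No alternative cause

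**Step 1: does the section cited by 6.6 cover the withholding triggers?** The profiles below are illustrative and chosen to isolate each trigger. They assume that no alternative cause has been identified. Enzyme, bilirubin and ALP values are multiples of ULN.

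| Profile | ALT | Bilirubin | INR | ALP | 8.4.6.1 | 8.4.6.2 |
|---|---|---|---|---|---|---|
| A | 9 | 1.0 | 1.0 | 1.0 | Trigger 1: withhold | Not met (bilirubin/INR) |
| B | 6, for 3 weeks | 1.0 | 1.0 | any | Trigger 2: withhold | Not met (bilirubin/INR) |
| C | 4, with nausea | 1.0 | 1.0 | any | Trigger 4: withhold | Not met (bilirubin/INR) |
| D | 4 | 2.5 | any | 2.0 | Trigger 3: withhold | Not met (ALP) |
| E | 4 | 2.5 | any | 1.0 | Trigger 3: withhold | All four met |

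Each of the four triggers has profiles that the cited section does not reach. Triggers 1, 2 and 4 are missed whenever bilirubin and INR stay at or below their cut-offs; trigger 3 is missed when ALP is 2 × ULN or more. The table shows coverage only and says nothing about how often such cases occur.

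**Step 2: does anything else in 8.4.6.2 rescue the citation?** Its closing paragraph mentions withholding once, where an alternative cause has been identified. It leaves the choice to case-by-case judgement with the Medical Monitor and gives no thresholds. It does not supply the withholding criteria that 6.6 promises.

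**Step 3: compare 7.1 with 8.4.6.2 for profile E.** Section 7.1 names the 8.4.6.2 conditions as its own condition, so the two sections address the same subject. One makes stopping a matter for consideration; the other directs it.

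**Step 4: does 8.4.6.1 close the gap in practice?** Nearly always. A subject who meets all four 8.4.6.2 criteria with ALT or AST above 3 × ULN also meets trigger 3, so drug is already withheld. Rechallenge needs an alternative cause, which criterion 4 rules out, so he has no stated route back to drug. One edge remains. At exactly 3 × ULN, with bilirubin > 2 × ULN, ALP below 2 × ULN and no alternative cause, criterion 2 (≥ 3) is met but trigger 3 (> 3) is not. If no other trigger applies, only 8.4.6.2 governs, and 7.1 softens it.

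**The case against.** The strongest reply is that neither slip changes what happens to a subject. Section 6.6 does not say that withholding is confined to 8.4.6.2. Section 8.4.6.1 depends on no pointer, sits directly above 8.4.6.2, and is cited correctly in the body of 8.4.6. Safety concerns go at once to the Medical Monitor, liver events that require withholding are reported within 24 hours, and 7.1 itself fixes the reason for discontinuation as AE. Both 7.1 and 8.4.6.2 use the word should, and the no-alternative-cause criterion is a clinical judgement in any event.

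Most of this stands as a limit on harm and is why the point ranks as minor. It is fair to call the 6.6 half a wrong pointer; the direct conflict of instruction is in 7.1. It is also fair that hand-picked profiles measure no risk.

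The reply does not make either text correct. Fixing the reason as AE does not settle whether the subject counts as discontinued, and 7.2 attaches study withdrawal to that status. Being told to consider stopping and being told to stop permanently remain different instructions for one patient.

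**Conclusion.** Both inconsistencies are present in the operative text. Section 6.6 cites the wrong subsection for withholding, and 7.1 is weaker than 8.4.6.2 for the case that both describe.

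The size is minor. Actual exposure should rarely differ, on the assumption that sites read 8.4.6.1 in its own right. The documents give no expected rate of such liver abnormalities, so no number of affected subjects can be stated. The one configuration in which 8.4.6.1 may give no backstop is ALT or AST at exactly 3 × ULN with the other Hy's-law criteria met, which should be rare. Sample size, power, type I error and the efficacy analysis are not affected.

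**What to change.** - **6.6:** cite 8.4.6.1 for temporary withholding and 8.4.6.2 for permanent discontinuation.
- **7.1:** state that study drug is permanently discontinued when all 8.4.6.2 criteria are met, and keep the investigator's discretion only for the separate best-interest judgement.

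Leave every threshold as it is. Once 7.1 is firm, the exactly-3 × ULN case is settled by 8.4.6.2 alone.

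The cost is two wording corrections in the next amendment, with a clarification memo to sites in the meantime. SAE reporting, assessments and analyses do not change.

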7.2. Subject Discontinuation/Withdrawal from the Study

- Subjects who discontinue study drug will also withdraw from the study.
- A subject may choose to withdraw from the study at any time at his own request, or may be withdrawn at any time at the discretion of the investigator for safety, behavioral, compliance, or administrative reasons.
- If a subject withdraws consent for disclosure of future information, the Sponsor or designee may retain and continue to use any data collected before such a withdrawal of consent.
- If a subject withdraws from the study, he may request destruction of any blood or urine samples taken and not tested, and the investigator must document this in the site study records.
- Subjects who withdraw from the study will not be replaced (enrollment accounts for a predetermined dropout rate).

The Week 24/Early Withdrawal assessments will be completed when a subject withdraws or is withdrawn from the study, if possible (see Schedule of Assessments in [Section 1.3](#) and [Section 1.4](#)).

Reasons for discontinuation from the study include the following:

- AE
- Lack of efficacy
- Noncompliance
- Withdrawal of consent
- Lost to follow-up
- Physician decision
- Protocol deviation
- Death
- Screen failure
- Run-in Failure
- Other

7.3. Lost to Follow-Up

Should a subject fail to attend a required study visit, the site should attempt to contact the subject and re-schedule the missed visit as soon as possible. The site should also counsel the subject on the importance of maintaining the assigned visit schedule and ascertain whether or not the subject wishes to and/or should continue in the study based on previous non-compliance. In cases where the subject does not return for the rescheduled visit and cannot be reached to reschedule the missed visit, the site should make every effort to regain contact with the subject so that they can appropriately be withdrawn from the study and all dispensed study medication is returned. If the subject cannot be reached, the subject should be withdrawn from the study with a primary reason of “Lost to Follow-up”. Including at least three documented attempts to contact the subject (ie, phone, email, or certified letter). Efforts to establish the possible reason for discontinuation should be documented.

7.4. Early Study Termination

The Sponsor reserves the right to terminate the study for any reason. The study may be terminated early if the extent (incidence and/or severity) of emerging effects/clinical endpoints is such that the risk/benefit ratio to the study population as a whole is unacceptable. In addition, further recruitment in the study overall or at a particular study site may be stopped due to insufficient compliance with the protocol, Good Clinical Practice and/or other applicable regulatory requirements, procedure-related problems or the number of discontinuations for administrative reasons is too high.

8. Study Assessments and Procedures

Study procedures and their scheduled timepoints are summarized in the Schedule of Assessments ([Section 1.3](#) [Part 1] and [Section 1.4](#) [Part 2]). A detailed listing of study assessments by visit is provided in [Section 10.7](#). Site personnel should note the following:

- Protocol waivers or exemptions are not allowed; however, subjects who fail to meet eligibility criteria may be rescreened once, as appropriate. Any notable protocol deviations should be noted and raised to the Sponsor's or designee's attention.
- Immediate safety concerns should be discussed with the Sponsor's designated Medical Monitor immediately upon occurrence or awareness to determine if the subject should continue or discontinue study drug.
- Adherence to the study design requirements, including those specified in the Schedule of Assessments, is essential and required for study conduct.
- Note that if done on-site (in person), PRO assessments will be completed prior to vital signs, and vital signs will be taken prior to blood draws.
- Certain study assessments and procedures may be performed remotely (eg, by telephone or video call). Refer to [Section 8.6](#) for additional details.

8.1. Baseline Procedures

8.1.1. Informed Consent

Documented consent must be obtained from each potential subject prior to participating in any study procedures according to the process described in [Section 10.1.3](#).

8.1.2. Assignment of Subject Number

All subjects who sign the ICF will be assigned a unique subject number by IWRS. This number will be used to identify the subject throughout the study. Subjects who are rescreened will be assigned a new subject number. If a new subject number is assigned, the subject will be linked to both subject numbers.

8.1.3. Screening

All screening evaluations must be completed and reviewed to confirm that potential subjects meet all eligibility criteria. The investigator will maintain a screening log to record details of all subjects screened and to confirm eligibility or record reasons for screening failure, as applicable. Inclusion and exclusion criteria ([Section 5.1](#) and [Section 5.2](#)) will be reviewed by the investigator or qualified designee at Screening, the start of the Run-in Period, and the start of the double-blind Treatment Period.

Subjects who fail to meet entry criteria may be rescreened **once**. (See [Section 8.1.2](#) regarding assignment of subject number.)

The Screening period may also be used for washout of prohibited medications (see [Section 6.5.1](#)).

8.1.4. Medical History

A medical history will be obtained by the investigator or qualified designee. Medical history will include all chronic and ongoing conditions, regardless of year diagnosed, surgical history, and substance abuse history. All events occurring after the subject signs the ICF will be recorded as AEs.

8.1.5. Demographics

Demographic data collection will include sex, age, race, and ethnicity.

8.1.6. Prior and Concomitant Medications

Prior OAB and BPH medications, as well as ongoing (concomitant) medications will be recorded beginning at the signing of the ICF and continuing until the Safety Follow-up call (5 days after the last dose of study drug).

8.1.7. Inclusion and Exclusion Post Placebo Run-In

All Inclusion and Exclusion criteria are to be rechecked for eligibility at the end of Placebo Run-In (prior to randomization). Specific inclusion criteria to be checked upon completion of the Placebo Run-In will include:

- Laboratory assessments (as defined in [Section 5.1](#))
- 3-day Bladder Diary review to confirm:
 - average of ≥ 8 but ≤ 20 micturition episodes per day
 - average of ≥ 3 urgency episodes per day over the 3-day diary period
 - average of ≥ 2 nocturia episodes per night
- IPSS total score of ≥ 8
- PVR volume value of < 100 mL

Specific exclusion criteria to be checked upon completion of the Placebo Run-In will include:

- Laboratory assessments (as defined in [Section 5.2](#))

- 24-hour urine volume > 3,000 mL based on 3-day Bladder Diary
- Qmax < 5.0 mL/second with a minimum voided volume of 125 mL
- Subject has taken < 80% or > 120% of the study medication during the Run-In period

8.2. Efficacy Assessments

Efficacy assessments will be collected as outlined in the Schedule of Assessments ([Section 1.3](#) and [Section 1.4](#)) in the form of 3-day Bladder Diary (refer to [Table 1](#)). Information collected in the diaries will be used for assessment of the primary and secondary efficacy endpoints related to the number of micturition, urgency, nocturia, and incontinence episodes per day as well as one 24-hr volume voided of urine. In addition, subjects will complete IPSS assessments, and [REDACTED] PGI, and [REDACTED] scores to assess quality of life endpoints.

Subjects will complete questionnaires either at the start of each required study visit (before vital signs and blood draws) or just prior to the visit if completing the forms remotely to assess subject-perceived symptom relief and health-related quality of life. The PRO questionnaires are provided in [Section 10.8](#). Additional information on the Bladder Diary and questionnaires is provided below.

